8.2. Statistical Analyses

8.2.1. Analysis of Secondary Endpoints

The efficacy variables are:

- Change from baseline in the Total Motor Score (TMS) assessment of the Unified Huntington Disease Rating Scale (UHDRS) after 6 and 12 months of treatment.
- Change from baseline in the Total Maximum Chorea (TMC) score of the UHDRS after 6 and 12 months of treatment.

- Clinical Global Impression-Improvement score after 6 and 12 months of treatment.

[figure not shown]
Descriptive statistics (n, mean, standard deviation, median, minimum and maximum) and 90% confidence interval will be provided to summarize results for each visit. The baseline and change from baseline values will be summarized as well by visit. A two-sided, paired *t*-tests at the 10% level of significance will also be used to summarize results. The paired *t*-tests will be done on all subjects and on three different groups. Baseline is defined as the final visit (Week 26) in the preceding double-blind study A8241021.

Clinical Global Impression-Improvement score after 6 and 12 months of treatment will be evaluated with descriptive statistics that includes n, mean, standard deviation (SD), median, minimum, and maximum. A two-sided, one-sample *t*-tests at the 5% level of significance will be applied to evaluate results.

Plots will be generated for mean change from baseline as well as mean over time as described in [Section 8.1](#).

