3. STUDY DESIGN

This study is a 12 month open label extension study of PF-02545920 20 mg dosed BID following study A8241021.

The study includes a Screening visit (V1) to assess eligibility followed by a Baseline visit (V2) and visits after 2 weeks, 4 weeks, 3 months, 6 months, 9 months, and 12 months of treatment. The final scheduled visit is a Follow-up visit 7-14 days after the last dose. Screening visit (V1) and Baseline visit (V2) will coincide with Week 19 and Week 26 Visits from study A8241021, respectively. For the Screening visit (V1) and Baseline visit (V2) procedures and assessments, the investigator will use data collected during Week 19 and Week 26 visits for study A8241021, respectively. Subjects, who meet study entry criteria, will be assigned to the 20 mg BID dose. During the 12-month treatment phase, subjects will return for study assessments at Week 2 (V3), Week 4 (V4), Month 3 (V5), Month 6 (V6), Month 9 (V7), Month 12 (V8), and for a Follow-up visit (V9).

Subjects, who were assigned to the 20 mg PF-02545920 dose group in the preceding A8241021 study, will continue to receive 20 mg PF-02545920 in this study without any titration. All other subjects will be titrated to the 20 mg BID dose as follows: 5 mg BID for 7 days, 10 mg BID for 7 days, 15 mg BID for 7 days, then 20 mg BID for the remainder of the treatment phase. Titration is in place to reduce incidence of AEs, frequent monitoring is in place for neutropenia, and an option for de-escalation by 5 mg decrements (temporary or

permanent) will be available should the investigator consider the AE intolerable (see Guidance on clinical management of subjects with acute extrapyramidal symptoms, Appendix 1).

Subjects who are discontinued (Early Termination) at or after Day 14 should complete as many of the Month 12 (V8) assessments as possible. Subjects should return to complete the Follow-up visit whenever possible.

Based on the total number of 260 subjects expected to be randomized in study A8241021, up to 260 subjects may take part in this open label extension.

[figure not shown]
[figure not shown]

Figure 1. Study Design Schematic

20 mg BID PF-02545920 (up to 260 subjects)

- Titration schedule for subjects previously not assigned 20mg PF-02545920:
 - 5mg BID x 7 days
 - 10mg BID x 7 days
 - 15mg BID x 7 days
 - 20mg BID to Month 12

5mg step de-escalation option available for intolerable AE

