4.3. Randomization Criteria

Once subjects have satisfied all selection criteria, they will be assigned a randomization number that will determine whether they will undergo blinded titration to 20 mg BID (subjects in the placebo and 5 mg BID arm in study A8241021) or continue the same dose (subjects already in the 20 mg BID arm in study A8241021) (See STUDY TREATMENTS).

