5.2. Breaking the Blind

All subjects will receive 20 mg PF-02545920 BID starting on Day 22. The initial titration period between Day 1 and Day 22 will be double blind.

The method for breaking the blind will be an electronic process via IRT. At the initiation of the study, the study site will be instructed on the method for breaking the blind. Blinding codes should only be broken in emergency situations for reasons of subject safety. The responsibility to break the treatment code in emergency situations resides with the investigator. Whenever possible, it is requested the investigator or sub-investigator consult with a member of the study team prior to breaking the blind. When the blinding code is broken, the reason must be fully documented and entered on the case report form (CRF)/data collection tool (DCT) and the Sponsor is to be notified.

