4. HYPOTHESES AND DECISION RULES

4.1. Statistical Hypotheses

The primary trial variables examine long-term safety and tolerability of therapy with 20 mg BID of PF-02545920. The primary analysis of long-term safety will be focused on Adverse events, weight, vital signs (pulse, blood pressure and body temperature), electrocardiogram (ECG), clinical laboratory findings (hematology, biochemistry and urinalysis), suicidal ideation and behavior (SIB) assessments and white blood count (WBC) and absolute neutrophil count (ANC). No formal statistical hypothesis will be conducted for the primary trial variables.

The secondary efficacy variables are:

- *Change from baseline in the Total Motor Score (TMS) assessment of the Unified Huntington Disease Rating Scale (UHDRS) after 6 and 12 months of treatment.*
- *Change from baseline in the Total Maximum Chorea (TMC) score of the UHDRS after 6 and 12 months of treatment.*
- *Clinical Global Impression-Improvement score after 6 and 12 months of treatment.*

Change from baseline in change in TMS and TMC will be calculated, decreases indicate improvement. The null hypothesis is that the change from baseline to a certain time-point is greater or equal to 0. The corresponding alternative hypothesis is that change from baseline to a certain time-point is less than 0. If the true mean change from baseline is denoted by μ then the hypothesis tested will be:

$$\begin{aligned} H_0: \mu &\geq 0 \\ H_a: \mu &< 0 \end{aligned}$$

For *Clinical Global Impression-Improvement* (CGI-I) score a lower score indicates improvement. The null hypothesis is that the CGI-I value at a certain time-point is greater or equal to 4 (no change to very much worse). The corresponding alternative hypothesis is that the CGI-I value to a certain time-point is less than 4 (very much improved to minimally improved). If the true mean change from baseline is denoted by μ then the hypothesis tested will be:

$$\begin{aligned} H_0: \mu &\geq 4 \\ H_a: \mu_{PF} &< 4 \end{aligned}$$

Both the change from baseline for all subjects (pooled) and by three cohorts (defined by dose level in A8241021 study: PF-20mg, PF-5mg, or Placebo) will be analyzed.

Statistical hypotheses for exploratory endpoints will be specified in a similar fashion as above.

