4.2. Statistical Decision Rules

All one-sided tests for secondary and exploratory endpoints are described as to be performed using the nominal alpha-level of 0.025, this corresponds to a two-sided test with alpha-level of 0.05. In addition to the p-values, two-sided 95% confidence intervals will be provided.

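### The visible secondary efficacy tests are all single-sample (change against 0, CGI-I against 4); a supportive difference between the former A8241021 arms would be a cheap improvement

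*SAP*

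**What the plan says.** SAP 4.1 frames the secondary efficacy hypotheses as statements about one mean. For TMS and TMC, "The null hypothesis is that the change from baseline to a certain time-point is greater or equal to 0". For CGI-I, "The null hypothesis is that the CGI-I value at a certain time-point is greater or equal to 4". It adds that change for all subjects and "by three cohorts (defined by dose level in A8241021 study: PF-20mg, PF-5mg, or Placebo) will be analyzed".

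SAP 8.2.1 applies this with paired t-tests for TMS and TMC: the "tests will be done on all subjects and on three different groups". CGI-I is evaluated with a one-sample t-test. The visible secondary rows of the SAP 8.5 table list only these tests, with no model, covariate or stratum. SAP 8.1 tabulates and plots the three groups side by side, with a 90% interval for each group's own mean, but specifies no difference between groups and no interval for one.

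Protocol 9.2.2 is also single-sample for the secondary endpoints. It adds one exploratory test, which compares each subject's rate of change in TMS and TMC during the double-blind period with the rate in the open-label period. The visible SAP text does not carry this test.

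The cohorts come from a randomised study ("Based on the total number of 260 subjects expected to be randomized in study A8241021", Protocol 3). On entry to the extension, subjects meet the selection criteria and "they will be assigned a randomization number that will determine whether they will undergo blinded titration to 20 mg BID" or continuation of the same dose (Protocol 4.3). Protocol 5.2 states: "The initial titration period between Day 1 and Day 22 will be double blind".

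**The concern.** A change from Week 26 within one cohort is the sum of at least three parts: any drug effect, disease progression over 6 or 12 months, and the shift in patients and raters that comes with known-active, open-label dosing. Both documents describe HD as progressive, and the CGI-I is defined to rate change whatever its cause. A mean change of 0, or a CGI-I of 4, is therefore not what an inert drug would be expected to produce. Net improvement from expectation can yield a significant result without a drug effect, and progression can hide a real one. The pooled test has the same weakness.

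Two of the secondary objectives speak of efficacy on chorea and of improving the overall clinical impression. A reader of the final tables could take a significant paired t-test as an answer to those questions. Meanwhile the study holds a concurrent comparison that the visible plan does not use: ex-placebo subjects start 20 mg BID while ex-20 mg subjects continue it, at the same visits and on the same scales.

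**Working it through.** **Inputs.** Neither document gives an SD, an effect size or a power calculation for efficacy; 260 is only an upper limit on enrolment (Protocol 9.1). There is thus no planned figure to reproduce. Assumed: 70 subjects per cohort and a 6-month TMS change SD of 8 points (range 6 to 10). Negative values are improvement. The level is two-sided 10%, as SAP 8.2.1 sets for TMS and TMC, so the nominal chance of declaring improvement is 0.05.

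**Formulas.** One-sample t: SE = SD/√n, noncentrality = mean change/SE, n − 1 df. Two-sample t: SE = SD·√(2/n), noncentrality = difference/SE, 2n − 2 df. Each result is the noncentral t probability of significance in the direction of improvement.

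**Standard errors at SD 8.** One-sample: 8/√70 = 0.96. Difference: 8·√(2/70) = 1.35.

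**Inert drug, ex-placebo cohort, one-sample test.**
- Drift -1: noncentrality -1/0.96 = -1.05, probability 0.27 (0.40 at SD 6, 0.21 at SD 10).
- Drift -2: noncentrality -2/0.96 = -2.09, probability 0.67, unrounded 0.665 (0.87 at SD 6, 0.50 at SD 10).

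**True effect of -2 points.**

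| Shared drift | One-sample test | Ex-placebo minus ex-20 mg |
|---|---|---|
| 0 | 0.67 | 0.43 |
| +1 (progression) | 0.27 | 0.43 |

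The contrast has noncentrality -2/1.35 = -1.48 whatever the shared drift; its power is 0.63 at SD 6 and 0.32 at SD 10. The two tests have about equal power when net progression is 0.6 points: at that value the one-sample noncentrality is -1.4/0.96 = -1.46. Below it, the one-sample test is the more powerful.

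**Check in SD units.** With 75 per cohort (the cohort size mentioned in Protocol Appendix 1) and an inert drug, a favourable drift of 0.2 SD gives a within-cohort probability of 0.53 at two-sided 10% and 0.40 at two-sided 5%. With all 260 pooled, the figure at 10% is 0.94. In 40,000 simulated trials with a shared drift of 0.2 SD in either direction, the between-cohort test kept its level: 0.098 to 0.099 at 10%, and 0.049 to 0.050 at 5%.

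**Smaller numbers.** At an assumed 30 per cohort, the contrast has power 0.25 for an effect of -2 at SD 8, with SE 8·√(2/30) = 2.07.

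**Level.** SAP 4.2 tests at a one-sided level "using the nominal alpha-level of 0.025, this corresponds to a two-sided test with alpha-level of 0.05", whereas SAP 8.2.1 uses 10% for TMS and TMC. That needs reconciling separately; the problem described here is present at either level.

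**The case against.** This is an open-label safety extension. Efficacy is secondary, the first secondary objective only assesses motor function, and SAP 8.2.1 uses the TMS and TMC t-tests to summarise results. Each cohort's mean change is already shown with an interval, so a reader can derive a difference approximately. The exploratory slope comparison in Protocol 9.2.2 partly addresses progression for ex-placebo subjects. All of this stands and limits the weight of the point. However, the slope comparison does not address open-label expectation, and derivation by the reader does not replace a specified estimate with its interval.

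A reader might also infer that the between-cohort contrast is a fully randomised, rater-blinded and unbiased estimate of drug effect that should carry the efficacy conclusion. The documents do not support that:

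- Entrants must have completed A8241021 and been judged compliant. They are also screened on blood counts and drug-related serious events in that study unless the sponsor approves. This selection follows randomisation and may depend on dose.
- The stated blind runs from Day 1 to Day 22. No visible passage says the prior arm stays masked to Month 6 or 12, and CGI-I raters may see all clinical information.
- De-escalation is allowed, so the ex-20 mg cohort is not guaranteed a constant dose. Its change equals progression plus expectation only if its drug effect neither grows nor wanes after Week 26.
- Expectation may differ between subjects starting and subjects continuing the drug. The CGI-I question refers to the beginning of treatment, which is ambiguous for subjects already on 20 mg.
- With no net drift the contrast has less power than the one-sample test (0.43 against 0.67).

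Nor can a reader conclude that no such contrast exists anywhere: SAP 8.2.2 and part of the 8.5 table are redacted. The TMS, TMC and CGI-I rows of 8.5 are visible, however, and list only single-sample tests.

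**Conclusion.** The point holds as a cheap improvement. In the visible text, every test of TMS, TMC and CGI-I as a secondary endpoint is single-sample, and its null is not a null of no drug effect. A modest favourable drift of 1 point would raise the chance of declaring improvement with an inert drug from 0.05 to about 0.27, and progression of 1 point would cut the power for a true effect of -2 from 0.67 to 0.27. These sizes rest on the assumed cohort size, SD, drift and effect; the direction does not.

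The between-cohort difference cancels whatever drift the cohorts share. It estimates starting versus continuing 20 mg among selected A8241021 completers, and reads as drug effect only if drift is shared and the ex-20 mg effect is stable after Week 26. It therefore belongs beside the planned summaries as supportive evidence, not as the sole basis of the efficacy statement.

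**What to change.** In SAP 8.2.1 and 8.5:

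- Add, as a supportive analysis, the ex-placebo minus ex-20 mg and ex-5 mg minus ex-20 mg differences in TMS and TMC change from Week 26 at Months 6 and 12, with confidence intervals. Treat Week 4 as exploratory, since it is not a secondary endpoint time.
- Use an ANCOVA with A8241021 arm as factor and the A8241021 Week 0 score as covariate. The Week 26 score is measured after randomisation and may already carry drug effect in the ex-20 mg arm, so it should not be the covariate.
- Give the same between-cohort difference for CGI-I as exploratory.
- Label the single-sample t-tests descriptive and not evidence of drug effect.
- Tabulate Week 0 and Week 26 characteristics by cohort, so that selection into the extension can be seen.
- State the limits with the result: starting versus continuing 20 mg among completers, shared drift and a stable ex-20 mg effect assumed, and no documented masking of prior arm after Day 22.

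The cost is SAP wording and one model on data already held. The interval is wider (SE about 1.35 against 0.96 points under the assumptions above), and wider still if the unexpected termination, with early-termination visits from 16 December 2016 left out of the summaries (SAP 8.1), reduces the numbers at Months 6 and 12. Because the addition would follow that termination, it should be identified as such.

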8.2.2. CCI

CCI

8.3. Analysis of Safety Data

8.3.1. Safety Analysis

A set of summary tables will be produced to evaluate any potential risk associated with the safety and toleration of administering PF-02545920.

The safety and other endpoints detailed here will be listed and summarized in accordance with sponsor reporting standards, where the resulting data presentations will consist of subjects from the safety analysis set. All safety endpoints will be summarized for all subjects as well as separated by three groups (ie, from PF 20mg, from PF 5mg, and from Placebo).

8.3.2. Treatment and Disposition of Subjects

Subject evaluation groups will show end of study subject disposition and will show which subjects were analyzed for FAS, safety (adverse events and laboratory data), and pharmacokinetics. Frequency counts will be supplied for subject discontinuation(s).

Data will be reported in accordance with the sponsor reporting standards.

8.3.3. Demographic Data and Clinical Examination Data

A breakdown of demographic data will be provided for age, race, weight, body mass index and height. Each will be summarized by sex at birth and ‘All Subjects’ in accordance with the sponsor reporting standards.

Medical history will be summarized and listed.

8.3.4. Discontinuation(s)

Subject discontinuations, temporary discontinuations or dose reductions due to adverse events will be detailed and summarized.

Data will be reported in accordance with the sponsor reporting standards.

8.3.5. Adverse Events

Adverse events will be reported in accordance with the sponsor reporting standards.

8.3.6. Suicidal Ideation and Behavior

A frequency distribution of C-CASA scores (predose/post dose) will be reported. No hypotheses associated with the C-SSRS or C-CASA scales will be tested.

The denominator used in the percentages will be the number of subjects assessed for suicidal ideation and behavior (SIB). For worsening, the denominator would include the subset of subjects who had any level of suicidality reported at baseline. For new onset, the denominator would include the subset of subjects with no suicidality reported at baseline.

A subject listing of C-CASA categories as well as the underlying C-SSRS scale data will be presented.

In addition, a summary table with the number and percent of subjects within each C-CASA category at baseline, and at any time post-baseline without regard to baseline will be reported.

8.3.7. Laboratory Data

Laboratory data will be listed and summarized by treatment in accordance with the sponsor reporting standards. Baseline is as defined in [Section 6.3](#).

A listing of subjects who meet any of the study stopping criteria for WBC or ANC counts will be presented.

8.3.8. Physical Exam/Weight

Physical examination data will be presented in a data listing and summary table using counts and percentages. Summary of new/intensified physical examination findings from Baseline to Month 12/ET will be presented.

Body weight absolute values and change from baseline will be summarized using descriptive statistics.

8.3.9. Vital Signs

Absolute values and changes from baseline in standing, supine and postural changes for systolic and diastolic blood pressure and pulse rate will be summarized, time postdose and day, according to sponsor reporting standards. Tables will be paged by parameter.

Baseline will be defined as the predose recordings on Day 1(V2).

Maximum absolute values and changes from baseline for vital signs (for supine and standing) will also be summarized descriptively by using categories as defined in [Appendix 1](#). Numbers and percentages of subjects meeting the categorical criteria will be provided. All planned and unplanned postdose timepoints will be counted in these categorical summaries. All values meeting the criteria of potential clinical concern will be listed.

Standing vital signs will be listed only.

8.3.10. ECG

Absolute values and changes from baseline in PR, QT, QRS, heart rate (RR) and QTcF will be summarized, time postdose and day using sponsor reporting standards. Tables will be paged by parameter.

ECG endpoints and changes from baseline (QTcF, PR, QRS) will also be summarized descriptively by using categories as defined in [Appendix 1](#) (for QTc these correspond to ICH E14¹). Numbers and percentages of subjects meeting the categorical criteria will be provided. All planned and unplanned postdose timepoints will be counted in these categorical summaries. All values meeting the criteria of potential clinical concern will be listed.

Listings of subjects with any single postdose value ≥ 500 msec will also be produced for QTcF.

8.3.11. Prior and Concomitant Treatments

All concomitant medication(s) as well as non-drug treatment(s) will be provided in the listings.

Frequency and type of medication will be summarized categorically.

[figure not shown]
8.3.12. Screening and Other Special Purpose Data

Serum FSH concentrations and urine drug screen will be obtained at screening (for drug screen, and at any time at the discretion of the investigator).

8.4. **CCI**

8.4.1. **CCI**

CCI

8.5. Summary of Efficacy Analyses

Endpoint	Analysis Set	Statistical Method	Model/ Covariates/ Strata	Missing Data	Interpretation
Δ from Baseline UHDRS Total Motor Score	FAS	Paired t -test	NA	Excluded	Secondary Analysis
Δ from Baseline UHDRS Total Maximum Chorea Score	FAS	Paired t -test	NA	Excluded	Secondary Analysis
CGI-I CCI	FAS	One-Sample t -test	NA	Excluded	Secondary Analysis

Endpoint	Analysis Set	Statistical Method	Model/ Covariates/ Strata	Missing Data	Interpretation
CCI					

Appendix 1. Categorical Classes for ECG and Vital Signs

Categories for QTcF

QTcF (ms)	450≤ max. <480	480≤ max. <500	max. ≥500
QTcF (ms) increase from baseline	30≤ max. <60	max. ≥60	

Categories for PR and QRS

PR (ms)	max. ≥300	
PR (ms) increase from baseline	Baseline >200 and max. ≥25% increase	Baseline ≤200 and max. ≥50% increase
QRS (ms)	max. ≥140	
QRS (ms) increase from baseline	≥50% increase	

Categories for Vital Signs

Systolic BP (mm Hg)	min. <90	
Systolic BP (mm Hg) change from baseline	max. decrease ≥30	max. increase ≥30
Diastolic BP (mm Hg)	min. <50	
Diastolic BP (mm Hg) change from baseline	max. decrease ≥20	max. increase ≥20
Supine pulse rate (bpm)	min. <40	max. >120
Standing pulse rate (bpm)	min. <40	max. >140

Appendix 2. C-SSRS Mapped to C-CASA

Table 1. C-CASA Suicidality Events and Codes

Event Code	Event
1	Completed suicide
2	Suicide attempt
3	Preparatory acts towards imminent suicidal behavior
4	Suicidal ideation
5	Self-injurious behavior, intent unknown
6	Not enough information, fatal
7	Self-injurious behavior, no suicidal intent
8	Other, accident, psychiatric; mental
9	Not enough information, non fatal

* Note: Event Codes 5, 6, 8 and 9 are not applicable to prospectively collected data

Table 2. C-SSRS Mapped to C-CASA - Suicidality Events and Codes

C-CASA Event Code	C-CASA Event	C-SSRS Response
1	Completed suicide	As captured in the safety database
2	Suicide attempt	“Yes” on “Actual Attempt”
3	Preparatory acts towards imminent suicidal behavior	“Yes” on any of the following: 
 • “Aborted attempt”, or • “Interrupted attempt”, or • “Preparatory Acts or Behavior”
4	Suicidal ideation	“Yes” on any of the following: 
 • “Wish to be dead”, or • “Non-Specific Active Suicidal Thoughts”, or • “Active Suicidal Ideation with Any Methods (Not Plan) without Intent to Act”, or • “Active Suicidal Ideation with Some Intent to Act, without Specific Plan”, or • “Active Suicidal Ideation with Specific Plan and Intent”
7	Self-injurious behavior, no suicidal intent	“Yes” on “Has subject engaged in Non-suicidal Self-Injurious Behavior?”

